**The purpose of this study is to incorporate feedback from cancer patients and providers to adapt, implement, and test**

an intervention. The intervention aims to prompt screening for financial distress, facilitate discussions about care costs with cancer patients, support health insurance selection, and ultimately reduce cancer patients' financial toxicity associated with cancer care [1-3]. This intervention is an online decision tool called I Can PIC (Improving Cancer Patients' Insurance Choices).

This study will evaluate I Can PIC's impact on patient care among newly-diagnosed patients with gynecologic, colorectal, or lung cancer. At the start of Aim 2, we will conduct a historic control survey of 100 patients with newly-diagnosed gynecologic, colorectal, or lung cancer to explore whether and how treatment costs are discussed with them. We will then conduct a brief training with oncologists to talk about screening for financial distress and discussing costs with patients. The training will consist of a brief 15 min presentation delivered in-person or virtually. Next, we will conduct a pilot intervention study where patients will complete I Can PIC, then complete a survey after their next oncology appointment. 3-6 months from recruitment, patient participants will complete a follow-up survey. 3 and 6 months after beginning recruitment, we will give the providers real-time feedback about how often they screened for financial distress and referred patients to I Can PIC.

**1.4** Specify your research question(s), study aims or hypotheses:

We propose to modify the I Can PIC decision aid based on stakeholder feedback and to implement it as part of usual care, along with screening for financial toxicity and cost discussions.

The goal of this study is to evaluate the refined I Can PIC's impact on gynecologic, colorectal, and lung cancer care using a between subjects design.

**1.5** Background and significance and/or Preliminary studies related to this project:

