- Any randomization, if applicable
- What participants will be asked to do/what happens in the study (in sequential order)
- The time period over which procedures will occur
- Long-term follow-up and how it occurs

At the start of this study, we will conduct a historic control survey of 100 recently diagnosed gynecologic, colorectal, and lung cancer patients. They can complete the survey in-person, over the phone, or online. The survey will take approximately 15 minutes to complete. It will ask about their knowledge of health insurance and confidence communicating about care costs. WU research staff will collect participants' distress assessment data, insurance status and other health conditions data from the electronic medical record in EPIC. At the time of enrollment, WU research staff will confirm participants' contact information (telephone/address). If they give us permission to email them we will document this in our records. They will receive a \$10 gift card as a thank you for their time.

Then, we will train 15 BJC gynecologic, colorectal, and lung cancer care providers in using I Can PIC and discussing costs with patients in a brief 15 min presentation that can be delivered in-person or virtually. Providers will complete a survey before and after their brief training at the start of the study. These surveys will take approximately 5-10 mins to complete in total. During the study, at 3- and 6- months, we will give providers on the percent of time that they screened for financial distress and referred patients to I Can PIC. This information is collected from the patient participants' surveys. At the end of the study, we will examine adoption, implementation, and maintenance measures. Providers will receive a \$50 gift card at the end of the study.

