Next, we will recruit 100 gynecologic, colorectal, and lung cancer patients of the providers we trained over a 9 month period. At the time of enrollment, WU research staff will confirm participants' contact information (telephone/address). If they give us permission to email them we will document this in our records. Next, they will use I Can PIC. This will take approximately 10-15 mins. After their next appointment with their provider, they will complete a brief survey online about their knowledge of health insurance and confidence communicating about care costs. WU research staff will provide their survey to participants via phone, email, or in-person. The survey will take about 10 mins. Participants will receive a \$20 gift card for reviewing I Can PIC and completing the survey.

Patient participants who choose to complete the study in person may view I Can PIC on a tablet provided by us in the clinic or at our office. Then after their appointment, they can complete the survey on a tablet provided by us in the clinic or at our office. If they choose to complete it over the phone, we will email them the link to I Can PIC and then call them when it is time to complete the survey. If they wish to complete it online, we will email them the link to I Can PIC, and then the survey after their appointment. WU research staff will collect participants' distress assessment data, insurance status and other health conditions data from the electronic medical record in EPIC. After 3-6 months, participants will receive a follow-up survey which they can complete in-person, online, or over the phone. WU research staff will collect participants' distress assessment data, insurance status and other health conditions data from the electronic medical record in EPIC. This survey will take about 10 mins to complete. Once it is done, we will mail them a \$10 gift card.

**1.14** Will participants be randomized?

No

**1.15** Will any of the following be used to collect information from the participant or others?

- Screening questions or screening/eligibility questionnaires
- Surveys
- Questionnaires
- Stimuli
- Any other written assessments

Yes

Attachment Name	Category	Version	Date Attached
P50_PI_post-intervention_survey_patients_05_20_2020.docx	Subject Data Collection Instruments	5	05/20/20
P50_PI_3-6 month follow-up_survey_patients_05_20_2020.docx	Subject Data Collection Instruments	6	05/20/20

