**1.22** Provide a summary of the analysis methods you will use, including, if applicable, the data points or outcomes you will analyze.

Descriptive statistics will be calculated for all variables and RE-AIM outcomes. Data will be examined for effectiveness outcomes between historic controls and intervention groups in a multivariable regression model controlling for up to 4 independent covariates (e.g. age, health literacy, insurance status, cancer type). The 3-6

month follow-up survey will be also conducted for the intervention group. The change in patient's outcomes between the first time point (after viewing I Can PIC) and the 3-6 month follow-up will be examined in a multivariable regression model controlling for up to 4 independent covariates (e.g. age, health literacy, insurance status, cancer type). We will examine the change in clinicians' responses to the surveys at the first time point and at the completion of the study in a regression model.

**1.23** Provide the rationale or power analysis to support the number of participants proposed to complete this study.  
All outcomes of patient participants are measured at screening for historic controls and at post-intervention for intervention groups. Power estimates are dependent on the effect size of each outcome, defined as the mean difference between two groups divided by the standard deviation. Using a two-tailed two-group t-test, a sample size of 80 patients with newly diagnosed breast, lung, or colorectal cancer in the intervention group and 80 historic controls has at least 80% power to detect an effect size of as small as 0.45 at a 0.05 level of significance. We will recruit up to 100 patients in each group (intervention and historic control) since we expect that some patients will drop out/not complete the surveys or follow-up. Powers were calculated using Power Analysis and Sample Size (PASS 15) software.

**1.25** Will any data from this project be stored for use in future research studies?  
No

**1.26** Does this project involve the collection or use of biological samples or genetic data?  
No

**1.27** Are you requesting institutional certification to contribute human data or samples to a repository or database for broad sharing (public or restricted access)?  
No

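### Does the 3-6 month change in intervention patients need a stated role and a fixed starting point before it can be analysed?

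*Combined protocol and SAP*

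**What the plan says.** All references are to the Protocol part of the combined document.

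Section 1.22 describes two patient analyses. The first is the comparison that carries the effectiveness claim: "Data will be examined for effectiveness outcomes between historic controls and intervention groups in a multivariable regression model". The second concerns intervention patients only. It takes the change in their "outcomes between the first time point (after viewing I Can PIC) and the 3-6 month follow-up will be examined in a multivariable regression model", again with up to four covariates given as examples. The same section says "Descriptive statistics will be calculated for all variables and RE-AIM outcomes" but does not say which RE-AIM outcome, if any, the change serves. Maintenance measures are mentioned once, in the provider paragraph of section 1.13.

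On timing, section 1.3 says "patients will complete I Can PIC, then complete a survey after their next oncology appointment", and then "3-6 months from recruitment, patient participants will complete a follow-up survey". Section 1.13 places the first survey after the next appointment as well, and goes on: "After 3-6 months, participants will receive a follow-up survey which they can complete in-person, online, or over the phone". It does not repeat the starting point.

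Historic controls complete one survey (section 1.13), and there is no randomization (section 1.14). Section 1.13 also has staff collect "distress assessment data, insurance status and other health conditions data from the electronic medical record in EPIC", once for controls and twice for intervention patients, each time in the description of a survey. The power statement in section 1.23 covers only the comparison of the two groups at one time point.

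**The concern.** Both surveys behind the change come after the tool has been used, and no comparison group is followed. The change can show whether scores hold or drift. It cannot show an effect of I Can PIC at 3-6 months. A result of that kind is usually given a label and a horizon, and here neither is explicit.

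The horizon looks loose in three ways. Section 1.3 counts from recruitment while section 1.13 names no origin. The first survey waits for an appointment with no date limit. Section 1.22 labels the first time point by viewing the tool, although the survey comes after the visit. If scores fade with time, the same rate of fading would give a different average change depending on the clock used and the wait for the visit.

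There is also a risk of misreading. With about 80 pairs, a non-significant change could be taken to mean that a benefit lasted when a sizeable loss has not been excluded. The undated chart extractions add to the impression that follow-up timing was left open.

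**Working it through.** **1. The plan's own figure.** Inputs from section 1.23: 80 per group, standardized difference 0.45, two-sided alpha 0.05. The noncentrality is 0.45 × √(80/2) = 2.85 on 158 degrees of freedom. Power is 80.8% by the exact t calculation and 81.2% by the normal approximation, so the stated minimum of 80% is reproduced. It belongs to the between-group comparison and does not depend on the follow-up survey.

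**2. Is there a second clock?** Section 1.3 names recruitment. Section 1.13 gives the same 3-6 months without an origin. Silence is compatible with section 1.3, and no passage starts the clock at the first survey. That alternative reading can be constructed, but the documents do not state it.

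**3. How far the gap between surveys could move.** Let F be the follow-up time, taken as uniform over 3 to 6 months from recruitment (assumed), and L the lag from recruitment to the first survey (assumed uniform; the documents give no value). The gap is G = F − L, with mean 4.5 − mean(L). For L up to 3 months, P(G < 3) = mean(L)/3. For illustration, let 0.45 SD be lost at a constant rate over 6 months, which is 0.45/6 = 0.075 SD per month (assumed).

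| Assumed lag L (months) | Range of G | Mean G | Share of G under 3 months | Mean loss (SD) |
|---|---|---|---|---|
| 0.25 to 1.5 | 1.5 to 5.75 | 4.5 − 0.875 = 3.625 | 0.875/3 = 29% | 0.075 × 3.625 = 0.27 |
| 0 to 0.5 | 2.5 to 6 | 4.5 − 0.25 = 4.25 | 0.25/3 = 8% | 0.075 × 4.25 = 0.32 |
| 0 (same day) | 3 to 6 | 4.5 | 0% | 0.075 × 4.5 = 0.34 |
| Clock from first survey | 3 to 6 | 4.5 | 0% | 0.34 |

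The short-lag rows cannot be ruled out. Section 1.13 lets patients who take part in person view the tool on a tablet in the clinic and answer the survey there after the appointment. Section 1.12 links mailing of letters to appointments booked ahead, with a call a week later, so contact is arranged around a coming visit. A minimum lag of 0.25 month leaves out the in-clinic route.

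The window that the plan states openly matters more than the clock. Under the same assumed rate, a gap of 3 months gives a loss of 0.225 SD and a gap of 6 months gives 0.45 SD. The choice of clock moves the mean by at most 0.34 − 0.27 = 0.07 SD in the table.

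**4. Precision of the change.** With 80 complete pairs, outcome SD 1 and correlation ρ between surveys (assumed), the 95% half-width is t(0.975, 79) × √(2(1 − ρ)) / √80. For ρ = 0.3, 0.5 and 0.7 this is 0.26, 0.22 and 0.17 SD, or 59%, 49% and 38% of 0.45. An observed change of zero would therefore not exclude a moderate loss. That limits what may be concluded, but section 1.22 draws no such conclusion.

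**5. Chart data.** Section 1.13 mentions extraction in the description of each survey, and section 1.22 does not name charted distress as an outcome of the change. The missing dates do not alter this analysis.

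**The case for a change.** The strongest case for acting is that the gap stays unfixed even if recruitment is accepted as the origin. The first survey is undated, so the time between the two measurements varies by an amount the documents do not bound. Section 1.22 gives the change its own multivariable model, which is more than simple description, without saying what question it answers. On the longer assumed lag, a paired t-test at the mean loss has 53% to 87% power with 80 pairs (ρ 0.3 to 0.7), against 71% to 97% if the clock starts at the first survey. A few sentences would settle the matter, with no new patient contact.

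Part of this stands. The spacing is not bounded, the label in section 1.22 is looser than the procedure it refers to, and the role is not stated. The half-widths in step 4 are also sound given 80 pairs, and would widen with fewer.

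The power contrast does not stand. It needs a clock the documents never give, a lag that excludes the in-clinic route, linear loss of the whole 0.45 SD, and a test that section 1.23 never claims to power. If scores fall early and then level off, the spacing matters little. Interval length is not barred as a covariate, since those listed are examples. The feared inference from a non-significant result appears nowhere in the plan.

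**Conclusion.** No change to the plan follows. The 3-6 month change is a description within one group, and the plan does not present it as evidence that the tool works. No stated rule gives a wrong answer if followed. The timing texts differ in completeness rather than in substance, and the only named origin is recruitment.

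The size of any effect on the result is unknown from the documents. Under the assumptions above, the mean shift from the choice of clock runs from zero (same-day survey) to about 0.07 SD (lag of 0.25 to 1.5 months), and all of it depends on an assumed linear loss. An analyst would ordinarily report the observed days between surveys and the change with its 95% interval. The spacing is the difference between two survey dates, however the follow-up was scheduled; the documents do not list those dates as data items, so their availability is assumed. Stating a role in advance would be tidy, but the plan ranks none of its outcomes, so the lack of a label is not peculiar to this analysis.

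The conclusion would differ if the change were used to claim an effect at 3-6 months, or if a non-significant test were taken as proof of maintenance. The plan does neither.

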- In the phone screening survey we will collect age, language, cancer diagnosis, cancer type, and time since cancer diagnosis data to confirm eligibility.
- For those who choose to review the consent information sheet over the phone, we will ask for their email address after consent.

- For those who choose to review the consent information sheet online, we will ask for their email address after confirming their eligibility with the screening survey.
- On the screening log we will record age, cancer type, date of cancer diagnosis, cancer clinician name, phone number, email address (if participant gives permission), and mailing address. We will also note in the screening log if participants give us permission to email them.

**1.8.c** What is the plan for individual identifiers obtained to identify participants and, if applicable, those identifiers maintained on a screening log prior to consent?

Identifiers for those who do NOT enroll will be destroyed at the earliest opportunity, consistent with the conduct of the research (for example when recruitment and enrollment are completed.)

**1.8.d** Does the research team agree that the requested information will not be reused or disclosed to any other person or entity, except as required by law, for authorized oversight of the study, or for other research for which the use or disclosure of the requested information would be permitted by the HIPAA Privacy Rule?

Yes

**1.10** Describe where the consent discussion will occur (check all that apply):

- Private room or area
- By phone

**1.11** Participants and/or their legally authorized representative will have (check all that apply to the consent process and explain process in Question 1.12 below):

- As much time as they desire to consider enrolling in the study, including:
  - An opportunity to thoroughly review the consent materials with knowledgeable members of the research team, and with family and/or friends as appropriate
  - Sufficient time to have all of their questions answered

**1.12** Provide a description of the enrollment and consent process in sequential order and address EACH of the bulleted points below:

- Describe each study population separately including control population
- Describe when recruitment and consent materials are used
- Indicate how much time individuals will have to consider participation

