- Use THIRD person active voice. For example, "the principal investigator will identify potential participants, the study coordinator will discuss the study with participants over the telephone and schedule the first study visit, etc..."
- Describe the steps that will be taken by the research team to minimize the possibility of coercion or undue influence during the consent process

For the historic control survey, the WU research staff will screen the patients of participating providers through EPIC to identify potentially eligible patients. They will retrieve the phone numbers and mailing addresses of potentially eligible patients so WU research staff can contact them. When possible based on appointments scheduled in advance (e.g., not same-day add-ons), WU research staff will mail potential participants a letter explaining the study's purpose and procedures so they have background about the study to review before being approached for consent. A week after mailing the letter, WU research staff will contact candidates by telephone to review the study and assess interest and eligibility. To confirm eligibility, WU research staff will ask for the potential participants' age, comfort reading and writing in English, cancer diagnosis, and time since cancer diagnosis.

If the potential participant is eligible and interested, WU research staff will ask if the participant would prefer to complete the survey in-person, over the phone, or online at home. If the participant chooses to complete the survey over the phone, WU research staff will review the phone consent information sheet with the participant. If the participant chooses to complete the study online, WU research staff will record their permission to send them emails, and send them a test email to confirm the email given is correct. Once staff receive confirmation from the participant they will send a link to the survey, in which the consent information is on the first page of the survey. The participant will indicate consent by clicking to the next page. If the participant chooses to complete the survey in-person, WU research staff will review the informed consent document when they meet with them in person in a private room. The potential participant can take as much time as they would like to consider their participation.

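### Historic controls are surveyed at screening and intervention patients after their next oncology appointment, so the group comparison mixes the intervention package with the effect of a further visit

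*Combined protocol and SAP*

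**What the plan says.** Section 1.23 sets the measurement times for the comparison: "All outcomes of patient participants are measured at screening for historic controls and at post-intervention for intervention groups".

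For the intervention group, the summary in section 1.3 says that "patients will complete I Can PIC, then complete a survey after their next oncology appointment". The procedures in section 1.13 agree: "After their next appointment with their provider, they will complete a brief survey online".

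For the controls, section 1.12 describes a mailed letter and then a call: "A week after mailing the letter, WU research staff will contact candidates by telephone to review the study and assess interest and eligibility". Consent and a single survey follow. Section 1.13 says "At the start of this study, we will conduct a historic control survey of 100 recently diagnosed gynecologic, colorectal, and lung cancer patients" and allows completion in person, by phone or online, with no visit required first. Clinician training comes afterwards: "Then, we will train 15 BJC gynecologic, colorectal, and lung cancer care providers in using I Can PIC and discussing costs with patients".

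Section 1.22 compares the two groups on the effectiveness outcomes in a multivariable regression, "controlling for up to 4 independent covariates (e.g. age, health literacy, insurance status, cancer type"). Section 1.14 confirms that there is no randomisation. No section aligns the two survey times or comments on the difference.

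**The concern.** Without randomisation, the comparison relies on measuring both groups at the same point in their care. Here one group must have had an oncology visit since enrolment and the other need not have.

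The visit with a trained clinician belongs to the intervention package, so measuring intervention patients after it is reasonable. The matching comparator is then a usual-care visit at the same point, and the plan provides none. The effect that any further visit would have had is credited to I Can PIC and the training.

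The control survey is meant to explore whether and how treatment costs are discussed (section 1.3), and both surveys cover confidence in communicating about costs (section 1.13). Answers that depend on having had a visit are the most exposed. If the two groups also enter at similar times since diagnosis, intervention patients are measured later in their illness.

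This is the study's only between-group effectiveness comparison, and section 1.21 says the results will inform implementation in a hospital system.

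**Working it through.** **Timing, side by side**

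| | Historic controls | Intervention patients |
|---|---|---|
| Sequence | Letter, call a week later, consent, survey (1.12, 1.13) | Letter, call a week later, consent, I Can PIC, next appointment, survey (1.12, 1.13) |
| Visit required between consent and survey | No | Yes |
| Measurement point in 1.23 | Screening | Post-intervention |
| Time since diagnosis at entry (1.7) | Within 5 months | Within 5 months |

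The 5-month window limits the gap in elapsed time but does not align it. The covariates in section 1.22 are examples, and none is a timing variable. Date of diagnosis is available (section 1.8.b: "On the screening log we will record age, cancer type, date of cancer diagnosis, cancer clinician name"), but time since diagnosis is not named for the model.

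**The plan's own power figure**

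Inputs from section 1.23: two-sided two-sample t-test, alpha 0.05, 80 per group, effect size d = 0.45 SD.

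- Noncentrality: d × √(n/2) = 0.45 × √40 = 2.846, with 158 degrees of freedom and critical value 1.975.
- Power from the noncentral t distribution: 80.8%.

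This reproduces the stated figure of at least 80%. The sample size is sound; the problem is bias, which the power calculation does not address.

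**What a timing shift would do (illustration)**

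The documents give no value for the shift, so b below is assumed. Suppose the intervention has no effect and the timing difference alone moves the intervention mean by b SD. The chance of a significant result is the same power function evaluated at d = b.

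| b (SD) | b / 0.45 | 80 per group | 100 per group |
|---|---|---|---|
| 0 | 0% | 5% | 5% |
| 0.05 | 11% | 6.1% | 6.4% |
| 0.1 | 22% | 9.6% | 10.8% |
| 0.2 | 44% | 24.2% | 29.1% |
| 0.3 | 67% | 47.1% | 56.0% |

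For example, b = 0.2 at 80 per group gives noncentrality 0.2 × √40 = 1.265 and rejection probability 24.2%. A larger sample makes a false positive from this source more likely. A shift in the opposite direction would hide a real effect: a true 0.45 SD effect reduced by 0.2 leaves 0.25 SD, for which power at 80 per group is 34.9%.

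**Cost of the remedy in power**

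With unequal groups the noncentrality is d / √(1/n₁ + 1/n₂). All rows use d = 0.45 and 80 intervention patients.

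| Change | Power |
|---|---|
| 80 controls, no change | 80.8% |
| 75 controls | 79.5% |
| 70 controls | 78.0% |
| 80 controls, 10 fewer degrees of freedom | 80.7% |
| 80 controls, groups 0.5 SD apart in days since diagnosis | 78.4% |
| 70 controls, groups 0.5 SD apart in days since diagnosis | 75.5% |

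Losing 10 degrees of freedom costs less than 0.1 point before rounding (0.8075 to 0.8072). The last two rows use the variance inflation for a covariate on which two equal groups differ by δ within-group SDs, 1 + δ²/4 = 1 + 0.25/4 = 1.0625. They assume that δ = 0.5 and that the covariate explains none of the outcome variance. For 70 versus 80 the equal-group factor is a close approximation.

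**The case against.** The strongest reply is that the gap is narrower than it looks. Controls are patients of participating oncologists within 5 months of diagnosis, so many will have had visits already. Their letters go out, where possible, in relation to scheduled appointments, so some will be surveyed near a visit. This stands, and it limits the size of the bias. It does not remove it, because a further visit after enrolment is required in one group and only possible in the other.

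Second, the intervention cannot be judged before the visit with the trained clinician. That is correct, and it is why the remedy moves the control survey and leaves the intervention survey where it is.

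Third, the main survey content named in section 1.13 is insurance knowledge and confidence in discussing costs. An ordinary visit may move insurance knowledge little, and the survey items are not shown. This is fair: exposure will differ by outcome. Section 1.3 nevertheless makes cost discussion a subject of the control survey.

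Fourth, the shifts in the illustration are chosen and say nothing specific about this trial; at 0.05 SD the false-positive rate is only 6.1%. That also stands. The case rests on the mismatch in the design, and the figures show only how sensitive the result is.

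Finally, time since diagnosis is already permitted, because the covariates are examples. It is not prespecified, however, and no covariate replaces a usual-care visit that was never required before the control survey.

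**Conclusion.** The concern holds and should be fixed. Followed exactly, the plan lets the ordinary effect of a required further visit, and possibly of more elapsed time, enter its only between-group effectiveness comparison. The mismatch is established by the plan's own text.

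Its effect on the results is not established. Size and direction are unknown, and they depend on how many controls happen to be surveyed soon after a visit and on survey items that are not shown. If the shift were 0.1 to 0.3 SD, an assumption, it would equal 22% to 67% of the effect the study is sized to detect and would raise the false-positive rate from 5% to between 10% and 47% at 80 per group. As this is a pilot and the remedy is modest, the flaw is not fatal.

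**What to change.** 1. Survey each control after the next oncology appointment following consent, the same anchor as in the intervention group. Complete that survey before the control's clinician is trained, either by closing control enrolment early enough or by moving that clinician's training date. The order of controls first and training second does not change.
2. Record the survey date in both groups and prespecify days since diagnosis at survey as a covariate in the between-group model, raising the cap of four if needed. Take insurance status as of enrolment, because the tool is meant to support insurance selection and could change it. Stage and number of visits to date can be added if they are first put on the list of data collected from EPIC after consent. Stage is now listed only for identifying candidates, and visit count is not listed at all.
3. Reconcile section 1.22, which describes the first intervention time point as after viewing I Can PIC, with the post-appointment timing in sections 1.3 and 1.13.

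If controls have already been surveyed, carry out step 2 and state that the difference in recent visits remains as a limitation that adjustment does not remove.

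**Cost.** The control survey is delayed until the next appointment, some training dates may move, and a few more controls may not respond. Power falls from 80.8% to 78.0% with 70 evaluable controls, or to about 75.5% if the groups also differ by 0.5 SD in days since diagnosis. Recruiting up to 100 per group can offset part of this, although section 1.23 already intends that margin for dropout and non-completion. Days since diagnosis needs only the survey date, since the date of diagnosis is on the screening log.
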